# **10. SAFETY CONSIDERATION**

#### **10.1 Duration:**

Record the start and stop dates of the adverse experience. If less than 1 day, indicate the appropriate length of time and units.

# **10.2 Immediate Reporting of Adverse Experiences to the SPONSOR Serious Adverse Experiences**

Any serious adverse experience, including death due to any cause, which occurs to any subject after immunization throughout the period of the study, whether or not related to the investigational product, must be reported within 24 hours from when the site become aware to the government pharmaceutical organization (GPO) following appendix B: standard operating procedure reporting of serious adverse event, and to the WHO focal point.

All vaccine-related serious and unexpected adverse experiences will be reported on an expedited basis to regulatory agency (ies) but will remain blinded.

The Sponsor is responsible for informing the Data and Safety Monitoring Board (DSMB) of the occurrence of any SAE observed in a trial subject. Detailed description including required information, methods and specific timeframe will be provided in the appendix B: standard operating procedure reporting of serious adverse event.

# **10.3 Reporting of Pregnancy**

Women who become pregnant during the study period will be followed for safety until the and OMMITTEE the pregnancy.

APPROVED

All female volunteers will be individual interviewed to ensure the reliable birth control method which included a sexual history and/or the last menstruation period (LMP) and they will be informed of the urine pregnancy test result either negative or positive.

# 10.4 Possible risks, including preventive and alleviative measures

The participants will receive single dose of a seasonal trivalent inactivated split virion influenza vaccine [A/Michigan/45/2015 (H1N1)-pdm09, A/Hong Kong/4801/2014 (H3N2), and B/Brisbane/60/2008 virus strains], produced by The Government Pharmaceutical Organization (GPO), Thailand. The administration of study vaccine may cause the subject pain, redness or swelling/edema at the vaccine injection site. Some subjects may experience systemic reactions such as increased fatigue, headache, fever, arthralgia, myalgia, nausea/vomiting and ORS\*. As usual, these symptoms go away by themselves within 1-3 days. In extremely rare cases of high individual sensitivity allergic reactions could be observed. Collection of blood samples through venipuncture may also cause subjects some discomfort or pain, redness, swelling and/or hardness at the puncture site.

\*Potential indicators of oculo-respiratory syndrome (ORS): ORS was first noted to be associated with pandemic H1N1 vaccination and has since been reported in association with seasonal inactivated influenza vaccination as well. This acute post-vaccination syndrome presents with symptoms such as bilateral conjunctivitis (red eyes), facial swelling and respiratory symptoms (chest tightness, coughing, a sensation of throat closure, difficulty swallowing, hoarseness, wheezing or difficulty breathing). As the symptoms can mimic an allergic reaction, clinical investigators need to be aware of how to distinguish the two conditions as much as possible.

# **10.5 Prevention and treatment**

All enrolled participants must be verified healthy by medical history evaluation, physical examination. Additionally, in order not to enroll pregnant woman, urine pregnancy test must be performed at the screening visit and prior to study vaccination.

At the follow up visit, the assessment of vital signs, physical examination (if indicated by history) and clinical follow up will be performed and all reported adverse events would be assessed. The study investigators will be experienced in monitoring and managing the safety of participants.

The investigator or other physician in attendance will administer therapy as clinically indicated. All adverse events will be followed until resolved, or until a stable situation has been reached. Adverse events that occurred during the study and which had not resolved at the last study visit will be followed until they have abated, or until a stable situation has been reached.

# **10.6 Concomitant Medication**

Information regarding concomitant medication in association with an adverse event will be collected and recorded in the source document and CRF.

The information reported in the CRF for each medication will be limited to:

- Trade name
- Indication
- Dose/ Unit/ Route/ Frequency
- Start and stop dates

Homeopathic medication and contraceptives medication will be recorded in CRF

ETHICS COMMITTEE FACULTY OF TROPICAL MEDICINE MAHIDOL UNIVERSITY

APPROVED

#### **10.7 Other Unexpected Issues/Unanticipated Problems**

During study process, if there are any problems related to the trial (unanticipated problems), the Principal Investigator is responsible for reporting certain unanticipated problems to GPO, to discuss reasonable ways of handling the problem. The Principal Investigator is responsible for reporting any unanticipated problems that affect the health, welfare, or rights of study participants or that may impact the integrity of the study data to the ethics committees involved in the review of the research. The Principal Investigator should maintain written documentation of all unanticipated problems and their reporting and resolution.

# 11. DATA MANAGEMENT AND STATISTICAL ANALYSIS

#### **11.1 Study hypothesis**

**Immunogenicity:** A single dose of the GPO seasonal trivalent split, inactivated influenza vaccine will induce immune responses to each of the three vaccine antigens, which are non-inferior to active comparator vaccine.

**Safety**: A single dose of the GPO seasonal trivalent split, inactivated influenza vaccine will be safe and well tolerated in adults 18 to 49 years of age.

#### **11.2 Sample size calculation**

The sample size calculation was planned for a ratio of 2:1 between GPO Tri fluvac and active comparator vaccine respectively. The SAS 9.4 statistical software, was used to calculate the sample size needed for the study under the assumption of a non-inferiority trial for binary outcome endpoint.

According to the EMA recommendations for the co-primary endpoints, the sample size calculation was basing on the following primary endpoints:

- The difference in seroconversion rate of active comparator vaccine and Seroconversion rate of GPO Tri Fluvac should not exceed 10 percentage points.
- The difference in natural log of mean antibody titer between active comparator vaccine and GPO Tri Fluvac should not exceed 0.405, which is equivalence to the margin for GMT ratio = 1.5.

The sample size calculation was calculated using parameters of the three strains of influenza under the study, including H1, H3, and Flu B. The estimates for seroconversion and standard deviation of natural log of antibody titer were obtained from previous study, phase II study of GPO Tri Fluvac.

Influenza strain	Titer Visit	Treatment Group	Sero- conversion	Mean of ln(titer)	SD of ln(titer)
H1	Day 21	Vaccine	0.88	5.9728	1.08277
Н3	Day 21	Vaccine	0.535	5.36976	1.11926
Flu B	Day 21	Vaccine	0.865	4.75286	1.23306

The sample size calculation for non-inferiority test for proportions was performed with the margin of 0.1, assuming different seroconversion rate of the three influenza strain, and expected difference VED in seroconversion of the two groups is 0.000 with one-sided test alpha level 0.025 and power 0.8. VED Finally the sample size was adjusted for 7% not included in the ATP cohort. The required sample MITTEE size for this co-primary endpoint reached a total of 945 subjects: 630 for study vaccine group and cal MEDICINE 315 for comparator vaccine group.

wo group test of equivalence in proportions (targe unequal n s)				
	H1	H3	Flu B	
Test significance level, α	0.025	0.025	0.025	
(one- sided)				
Standard proportion, $\pi_{S}$	0.880	0.535	0.865	
Equivalence limit difference,	0.100	0.100	0.100	
$\pi_{T}$ - $\pi_{S}$ , $\Delta_{0}$				
Test expected proportion, $\pi_T$	0.880	0.535	0.865	
Expected difference, $\pi_T - \pi_S$ , $\Delta_1$	0.000	0.000	0.000	
Power (%)	80	80	81	
ns	125	293	134	
n T	250	586	276	
Ratio: n T / n S	2.000	2.000	2.000	
$\mathbf{N} = \mathbf{n}_{\mathrm{S}} + \mathbf{n}_{\mathrm{T}}$	375	879	414	
Adjusted 7% not included in the ATP cohort				
n S	134	315	148	
n T	268	630	296	
$\mathbf{N} = \mathbf{n}_{\mathrm{S}} + \mathbf{n}_{\mathrm{T}}$	402	945	444	

Two group test of equivalence in proportions (large unequal n's)

The sample size calculation for noninferiority test comparing two means was performed according to the standard deviation of natural log scale of antibody titer of the 3 influenza strains with the margin of 0.405 (equivalence to ln of GMT ratio at 1.5), assuming expected difference in mean of natural log scale of antibody titer between the two groups is 0.000 with one-sided test alpha level 0.025 and power 0.8. Finally the sample size was adjusted for 7% not included in the ATP cohort. The required sample size for the co-primary endpoint reached 354 in total: 236 for study vaccine group and 118 for comparator vaccine group.

Two group t-test of equivalence in means (unequal n's)			
	H1	H3	Flu B
Test significance level, α (one-	0.025	0.025	0.025
sided)			
Equivalence limit difference, $\Delta_0$	0.405	0.405	0.405
Expected difference, $\Delta_1$	0.000	0.000	0.000
$\Delta_0$ - $\Delta_1$	0.405	0.405	0.405
Common standard deviation, $\sigma$	1.082	1.119	1.233
Power ( % )	80	80	80
n1	85	91	110
n2	170	182	220
Ratio: n 2 / n 1	2.000	2.000	2.000
$\mathbf{N} = \mathbf{n}_1 + \mathbf{n}_2$	255	273	330
Adjusted 7% not included in the AT	P cohort		
n s	91	98	118
n T	182	195	236

APPROVED ETHICS COMMITTEE FACULTY OF TROPICAL MEDICINE MAHID OL UNIVERSITY 273 293 **354** 

Final sample sizes for the study after adjusted for 7% not included in the ATP cohort = 630:315

With 630 evaluable participants randomized to GPO Trifluvac vaccine, the study has 95% power to detect at least one vaccine associated AE if true incidence is 1.0%. This provides high probability of detecting common (1–10%) vaccine associated adverse events. If no vaccine-related SAE is observed, the study will be able to exclude events occurring at approximately  $\geq 0.58\%$  based on the upper bound of the one sided 95% Confidence Interval (CI). The precision of the estimate of AEs judged to be related to vaccine as bounded by 95% CI is presented in Table 3.

 Table 3 Exact 95% Confidence Intervals around Potential Number of Study Drug Associated

 Adverse Events

Sample size	Number of events	Two sided exact 95% CI
630	0	0 0.58
	1	<0.01 0.88
	2	0.03 1.14
	5	0.25 1.84
	10	0.76 2.90

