#### 11.3 Data Analysis

#### **11.3.1 General Data Analysis Considerations Analysis Populations**

All subjects who receive one vaccination will be included in the safety population. This population will be used in the evaluation of safety and tolerability.

The immunogenicity analysis will be conducted based on an intent-to-treat (ITT) analysis. The population for the intent-to-treat analysis is defined as all individuals in the trial. The intent-to-treat analysis will include individuals who do not comply with the protocol-defined treatment schedule; that is, the intent-to-treat analysis will include individuals who may not complete the vaccination and follow-up.

As there might be some individuals who did not comply with the protocol-defined treatment schedule, a per-protocol analysis (PPA) will also be conducted. The population for the per protocol analysis is defined as individuals who meet all inclusion and exclusion criteria, and complete the treatment schedule.

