# **11.4 Analysis of Safety Endpoints**

The safety profile of the GPO Tri Fluvac will be evaluated by the number and proportion of participants experiencing AEs by severity and relatedness to vaccination of the following five categories for all participants:

- A. Solicited local adverse events, including redness / erythema, swelling / induration, pain within 30 minutes of vaccination and over a 3-day period (Day 0-3) post-vaccination.
- B. Solicited systemic adverse events, including fever, fatigue, malaise, muscle aches, joint aches, chills, nausea, and headache within 30 minutes of vaccination and over a 3-day period (Days 0-3) post-vaccination.
- C. Unsolicited AEs occurring within 90 days post vaccination.
- D. SAEs occurring during the entire study period (Days 0-90).

Occurrences of all events will be reported and summarized according to event severity, as "any local AE", or "any systemic AE", and by relationship to administration of study product, as deemed by a blinded study clinician. Percentage of participants experiencing each reaction or event, or at least one reaction or event will be calculated along with two-sided exact 95% CIs. No statistical testing will be performed for unsolicited AEs; including SAEs. The percentage of participants with solicited AE and SAEs will be compared between vaccine and comparator groups and a two-sided p-value of 0.05 will be considered statistically significant.

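### Protocol 11.2 understates the chance of seeing a 1.0% adverse event among 630 recipients (99.8%, not 95%) and labels a two-sided 95% limit of 0.58% as one-sided

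*Protocol*

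**What the plan says.** After fixing the sample size, Protocol section 11.2 describes what the safety data can show. The paragraph opens "With 630 evaluable participants randomized to GPO Trifluvac vaccine" and states that "the study has 95% power to detect at least one vaccine associated AE if true incidence is 1.0" per cent. It then says that, if no vaccine-related SAE occurs, event rates of about 0.58% or more can be excluded, "based on the upper bound of the one sided 95% Confidence Interval (CI").

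Table 3 follows directly. It lists exact limits for 0, 1, 2, 5 and 10 events in 630 under the column heading "Two sided exact 95% CI". Its zero-event row runs from 0 to 0.58.

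Three other places bear on the point:

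- Section 11.3.1 defines who is counted: "All subjects who receive one vaccination will be included in the safety population".
- Section 11.4 plans the reporting of safety events: the percentage with each event or "at least one reaction or event will be calculated along with two-sided exact 95% CIs".
- The SAP (Study Synopsis, Primary Safety Endpoints) plans the same two-sided exact intervals. The SAP text repeats neither the 95% detection statement nor the 0.58% exclusion statement.

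**The concern.** The first sentence gives every input needed to check it: 630 people, 1.0% incidence, at least one event. At that incidence 6.3 events are expected, so the chance of seeing none is far below 5%, and a stated 95% looks wrong on sight.

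The second sentence gives the same number as Table 3 but a different sidedness. For zero events, the one-sided and two-sided 95% upper limits differ, so both labels cannot be right.

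These sentences and Table 3 are the protocol's only quantitative account of what the safety sample can detect or exclude, and safety is a primary objective. If the wording were carried into the study report, a zero-event result would be given the wrong confidence level.

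**Working it through.** **Inputs.** n = 630 Tri Fluvac recipients, 1.0% incidence, a threshold of one event, and 0 observed events for the exclusion statement, all from Protocol 11.2. Section 11.3.1 counts everyone vaccinated, so 630 is the right denominator, with no deduction for the 7% expected to fall outside the ATP cohort.

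**1. Detection probability**

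P(at least one event) = 1 − (1 − p)^n

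- At p = 0.01 and n = 630: 0.99^630 = exp(630 × ln 0.99) = exp(−6.332) = 0.0018, so P = 0.9982, or **99.8%** against the stated 95%. The Poisson approximation, 1 − exp(−6.3), also gives 0.9982.
- Number needed for 95% at 1.0%: ln(0.05)/ln(0.99) = 298.07, so **299** (0.94996 at 298, 0.95046 at 299).
- Incidence detected with 95% probability at n = 630: 1 − 0.05^(1/630) = **0.47%**.

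Other readings were tried to recover 95%:

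| Reading | Probability |
|---|---|
| n = 586 (before the 7% allowance), at least 1 event, 1.0% | 99.7% |
| n = 945 (both arms), at least 1 event, 1.0% | 99.99% |
| n = 315 (comparator arm), at least 1 event, 1.0% | 95.8% |
| n = 630, at least 3 events, 1.0% | 95.1% |
| n = 630, at least 1 event, 0.5% | 95.7% |

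The last three come close, but each contradicts the sentence: it names the 630 vaccine recipients, at least one event, and 1.0%.

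**2. Upper limit for 0/630**

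- Two-sided 95%: 1 − 0.025^(1/630) = 0.584%. This reproduces the plan's 0.58%.
- One-sided 95%: 1 − 0.05^(1/630) = **0.474%**.
- One-sided confidence actually attached to 0.58%: 1 − (1 − 0.0058)^630 = 97.4%.
- 0.58% would be a one-sided 95% bound only at n = ln(0.05)/ln(0.9942), about 515. At n = 586 the one-sided bound is 0.51%, so the size before the 7% allowance does not explain it either.

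**3. Which label is right**

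Exact (Clopper-Pearson) upper limits for n = 630, in per cent:

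| Events | Table 3 | Two-sided 95% | One-sided 95% |
|---|---|---|---|
| 0 | 0.58 | 0.584 | 0.474 |
| 1 | 0.88 | 0.881 | 0.751 |
| 2 | 1.14 | 1.142 | 0.996 |
| 5 | 1.84 | 1.842 | 1.661 |
| 10 | 2.90 | 2.900 | 2.678 |

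All five upper limits match the two-sided column and none matches the one-sided column. The table is right and the sentence above it is mislabelled.

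**The case against.** The strongest case on the other side concerns consequence rather than arithmetic.

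- **Nothing depends on either figure.** The 630:315 split comes from the H3 seroconversion calculation, the stopping rules in section 9.3 are event counts, and the safety analysis uses two-sided exact intervals. This stands, and it is why the point is minor.
- **The conclusion drawn is still true.** The protocol goes on to claim a high probability of detecting common (1–10%) events, and 99.8% supports that better than 95%. Read as a floor, 95% is not false. The first part stands. The second does not rescue the sentence, which gives a figure and not a minimum.
- **Table 3 resolves the sidedness where it occurs.** It does so for a careful reader, but the sentence still contradicts the table.
- **The authors may have misstated an input and not the probability.** The documents cannot show which value was intended, so it is fair to ask. On the inputs as printed, the probability is 99.8%.
- **Two Table 3 lower limits look truncated and not rounded:** 0.03 against 0.038 for 2 events, and 0.25 against 0.258 for 5 events. This is correct but trivial, and does not affect the upper limits used here.

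**Conclusion.** Both parts hold as minor errors in stated figures. On the printed inputs the detection probability at 1.0% is 99.8%, not 95%; put the other way, 630 recipients give a 95% chance of seeing an event with an incidence of about 0.47%, not 1.0%. The 0.58% limit for 0/630 is correct as a two-sided 95% upper limit and wrong as a one-sided one, which is 0.47%.

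Both slips are conservative, since they understate what the trial can detect or exclude. The calculation assumes independent events with a common incidence and that all 630 are vaccinated and followed for safety. With 586 the detection probability would still be 99.7%.

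**What to change.** Make two wording corrections in Protocol section 11.2:

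1. Replace the detection statement with: *With 630 participants receiving GPO Tri Fluvac, the probability of observing at least one vaccine-associated AE is 99.8% if the true incidence is 1.0% (95% if it is about 0.47%).* The authors should confirm that 1.0% and at least one event are the inputs they meant.
2. In the exclusion statement, keep 0.58% and change one-sided to two-sided. The text then agrees with Table 3, section 11.4 and the SAP. Keeping one-sided and giving 0.47% would also be numerically correct, but that bound appears nowhere in Table 3 and differs from the planned intervals, so it is the less tidy choice.

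The two truncated lower limits in Table 3 can be rounded to 0.04 and 0.26 at the same time. The cost is editorial only: the design, sample size, stopping rules and analyses do not change.

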#### 11.3 Data Analysis

#### **11.3.1 General Data Analysis Considerations Analysis Populations**

All subjects who receive one vaccination will be included in the safety population. This population will be used in the evaluation of safety and tolerability.

The immunogenicity analysis will be conducted based on an intent-to-treat (ITT) analysis. The population for the intent-to-treat analysis is defined as all individuals in the trial. The intent-to-treat analysis will include individuals who do not comply with the protocol-defined treatment schedule; that is, the intent-to-treat analysis will include individuals who may not complete the vaccination and follow-up.

As there might be some individuals who did not comply with the protocol-defined treatment schedule, a per-protocol analysis (PPA) will also be conducted. The population for the per protocol analysis is defined as individuals who meet all inclusion and exclusion criteria, and complete the treatment schedule.

#### Data considerations

All available data will be included in the data listings and graphical summaries. For the formal VED statistical analyses and summary statistics, all available data will be included as appropriate for the MITTEE analysis methods. Procedure to account for missing, unused or spurious data will be defined in the cal medicine mathematical medicine mathematical will be defined in the cal medicine mathematical medicine mathematical will be defined in the cal medicine mathematical medic

21/2

final data analysis report. Any data transformation that may necessarily be done will also be described in the final study report.

## Assessment of immune response

According to WHO and FDA guidelines, the antibody titres to corresponding vaccine strain of influenza virus will be analyzed by comparison of paired serums using HI assay.

The serum samples will be collected on Days 0 prior to vaccination, Day 21, and Day 90 and will be analyzed for presence of influenza-specific antibody using Hemagglutination Inhibition (HI) assay. HI antibody titers will be compared between pre- and post-vaccination serum samples.

Percentages of subjects with each immune response will be calculated along with 95% CIs using exact statistical methods. Geometric mean titers (GMTs) along with 95% CIs will also be calculated using the t-test. No multiplicity adjustment to the error rate, alpha, will be made.

The primary immunogenicity endpoint is based on the ATP cohort, and NI conclusion will be based on the outcome of this analyses.

The primary immunogenicity endpoints and analysis are as follows:

- Number and percentage of participants with seroconversion against each of the three vaccine antigens. Seroconversion is defined as a serum HI antibody titer meeting the following criteria:
  - Pre-vaccination titer <1:10 and a post-vaccination titer measured on Day 21 of ≥1:40; or

  - Pre-vaccination titer ≥1:10 and at least a four-fold increase in post-vaccination measured on Day 21.
- Geometric mean titers (GMTs) of serum HI antibodies pre- (Day 0) and post-vaccination (Day 21) for each of the three vaccine antigens.

In assessing the non-inferiority, the upper bound of the two-sided 95% CI on the difference between the seroconversion rates (Seroconversion rate of active comparator vaccine – Seroconversion rate of GPO Tri Fluvac) should not exceed 10 percentage points. For the other primary endpoint, the upper bound of the two-sided 95% CI on the ratio of the GMTs (GMT active comparator vaccine/GMT GPO Tri Fluvac) should not exceed 1.5.

In addition, the secondary immunogenicity endpoints and analysis include the following:

- Number and percentage of participants with a HI antibody titer ≥1:40 (seroprotective level) to each of the three vaccine antigens measured on Day 21 and Day 90.
- Number and percentage of participants who develop at least a four-fold increase in HI antibody titers to each of the vaccine antigen post-vaccination measured on Day 21 and Day 90 segregated by pre-vaccination HI antibody titers (<1:10 or ≥1:10).
- Geometric mean fold rises (GMFRs) of serum HI antibodies (post-vaccination/ pre-vaccination) for each of the three vaccine antigens.
- GMTs of serum HI antibodies pre- (Day 0) and post-vaccination (Day 2) and Day 90) for each of the three vaccine antigens segregated by pre-vaccination HI antibody titers OMMITTEE (<1:10 or ≥1:10).

• GMFRs of serum HI antibodies (post-vaccination/pre-vaccination) for each of the three vaccine antigens segregated by pre-vaccination HI antibody titers (<1:10 or ≥1:10).

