The proportions of seroconversion responders, at Day 21 between groups (vaccines or comparator) will be examined and compared to determine the effect of an inactivated trivalent influenza vaccine. The antibody titers of each group will also be presented as GMT. The 95% CI and *p*-value will be calculated and presented. Multivariate analysis will be performed as needed to explore potential confounders.

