Counts and percentages of subjects with solicited local and systemic reactions during the three days post-injection. In addition, all adverse events (AE) and serious adverse events (SAEs), and new onset of chronic diseases (NOCDs) will be collected for the entire study period. Specifically, the following safety parameters will be monitored and analyzed in terms of the number and proportion of participants reporting the following events will be assessed:

- Solicited local adverse events, including redness/erythema, swelling/induration, pain and limitation of arm movement within 30 minutes of vaccination and over the 3-day period post vaccination (Day 0-3).

- Solicited systemic adverse events, including fever, fatigue/malaise, muscle aches, joint aches, chills, nausea and headache within 30 minutes of vaccination and over the 3-day period post vaccination (Day 0-3).

- Unsolicited adverse events (AEs) occurring within 90 days post vaccination.

- Serious Adverse Events (SAE) occurring during the entire study period (Days 0-90).

Counts of all events will be reported and summarized according to event severity, as "any local AE", or "any systemic AE", and by relationship to administration of study product, as deemed by a blinded study clinician. Percentages of participants experiencing each reaction or event, or at least one reaction or event will be calculated along with two-sided exact 95% CIs. The percentage of participants with solicited AE and SAEs will be compared between vaccine and comparator groups and a two-sided p-value of 0.05 will be considered statistically significant.

Inferential analyses

GMT ratios (GMT active comparator vaccine/GMT GPO TRI FLUVAC) and difference of seroconversion rate (with two-sided 95% CI) related to the comparisons of interest will be computed. Acceptance value of GMT ratios at \leq 1.5 and/or difference of seroconversion rate at \leq 10% for the upper bound of the 95% CI will be considered for non-inferiority.

Secondary Immunogenicity Endpoints and analysis:

The secondary immunogenicity endpoints will be analyzed by the following:

- Number and percentage of participants with a HI antibody titer $\geq 1:40$ (seroprotective level) to each of the three vaccine antigens measured on Day 21 and Day 90.

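### Neither co-primary non-inferiority comparison is adjusted for Day 0 HI titre, which gives up precision on H3 seroconversion, the endpoint that sets the sample size

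*Protocol*

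**What the plan says.** Protocol section 11.3.1 (Assessment of immune response) bases the decision on upper 95% confidence bounds for the seroconversion difference and the GMT ratio. On the titres it says: "Geometric mean titers (GMTs) along with 95% CIs will also be calculated using the t-test". The SAP (Inferential analyses) adds only that GMT ratios and the "difference of seroconversion rate (with two-sided 95% CI) related to the comparisons of interest will be computed". The SAP shells for these results, TREF 02 to TREF 04, show no covariate.

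Adjustment is mentioned once, at the end of Protocol section 11.5: "Multivariate analysis will be performed as needed to explore potential confounders". No model or covariate is named, and the sentence is not tied to the non-inferiority decision.

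Day 0 titre appears in four other places:
- It is part of the seroconversion definition.
- It is the denominator of the GMFRs.
- It defines the secondary analyses split at 1:10, which have no combined stratified estimate.
- SAP TREF 4.8 compares Day 0 GMTs between arms.

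Randomisation (Protocol 5.3.1) uses permuted blocks, with no stratification by Day 0 titre described.

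**The concern.** Protocol section 3 requires non-inferiority for each antigen. H3 seroconversion is the tightest of these tests. In the earlier Tri Fluvac trial (Protocol 2.4, Table 1), H3 had the highest Day 0 GMT (51.16, against 19.39 for H1 and 9.97 for Flu B) and the lowest four-fold rise (53.5%, against 88.0% and 86.5%).

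Seroconversion depends on baseline by construction, because Day 0 titre sets the level that each person must reach. Its presence in the definition therefore does not adjust the comparison between arms. An arm that starts higher by chance will tend to seroconvert less and, if the two titres are positively correlated, to have a higher Day 21 GMT. The two co-primary results would then move in opposite directions. With adjustment left open, a borderline H3 result would invite argument over a model chosen after the data were seen.

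**Working it through.** **Inputs from the documents.** Protocol 11.2 states the seroconversion margin: "The difference in seroconversion rate of active comparator vaccine and Seroconversion rate of GPO Tri Fluvac should not exceed 10 percentage points". The ln-titre difference "should not exceed 0.405, which is equivalence to the margin for GMT ratio = 1.5". The expected difference is "0.000 with one-sided test alpha level 0.025 and power 0.8", and the size was "planned for a ratio of 2:1 between GPO Tri fluvac and active comparator vaccine". The H3 rate is 0.535. The SDs of ln Day 21 titre are 1.082 (H1), 1.119 (H3) and 1.233 (Flu B). Table 1 gives the H3 vaccine-arm GMTs (N = 200) as 51.16 (43.43 to 60.27) at Day 0 and 214.81 (183.77 to 251.09) at Day 21.

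**1. Reproduce the plan's size.** Comparator n = (1.960 + 0.842)² × 0.535 × 0.465 × (1 + 1/2) / 0.10² = 292.9, so 293 + 586 = 879, as printed. Dividing by 0.93 gives 315.05 and 630.1, against the printed 315 and 630.

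**2. Unadjusted power at 586/293.** The SE of the H3 difference is √[0.535 × 0.465 × (1/586 + 1/293)] = 0.0357, a 95% half-width of 7.0 points. Power = Φ(0.10/0.0357 − 1.96) = 80.0%. The same formula gives 99.0% for H1 and 98.3% for Flu B.

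For GMTs, SE = SD × √(1/586 + 1/293) = 0.0774, 0.0801 and 0.0882, and Φ(0.405/SE − 1.96) = 99.9%, 99.9% and 99.6%. Lost precision therefore matters only for H3 seroconversion.

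**3. Size of chance imbalance in H3 Day 0 titre.** SD = ln(60.27/43.43) / (2 × 1.972) × √200 = 1.175. The same step on the Day 21 interval returns 1.119, matching the stated SD. The SE of the arm difference is 1.175 × √(1/586 + 1/293) = 0.084. The 95% chance range is ±0.165 ln units, a Day 0 GMT ratio within a factor of 1.18.

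**4. Effect of adjustment.** If Day 0 titre explains a share R² of seroconversion variance in each arm, the variance of the difference is multiplied by about (1 − R²).

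R² is not in the documents. I modelled ln Day 0 and ln Day 21 titres as bivariate normal with the GMTs and SDs above, on two-fold dilutions from 1:10 with values below 10 set to 5, and applied the Protocol's seroconversion definition. The correlation is assumed. The shift is the model's linear slope of seroconversion on ln Day 0 titre times 0.165.

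| Assumed correlation | Model H3 rate | R² | H3 power | Shift for a 1.96-SE imbalance (points) |
|---|---|---|---|---|
| 0.2 | 0.60 | 0.275 | 91% | 3.5 |
| 0.3 | 0.61 | 0.24 | 90% | 3.3 |
| 0.5 | 0.63 | 0.17 | 87% | 2.7 |
| 0.7 | 0.66 | 0.11 | 84% | 2.0 |

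**5. Check on the model.** It predicts a rate of 0.60 to 0.66 against the observed 0.535. Lowering its Day 21 mean until it gives 0.535 (model GMT about 165) leaves R² at 0.11 to 0.27 and the shift at 2.1 to 3.6 points.

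**6. In participants.** 879 × (1 − 0.11) = 782 and 879 × (1 − 0.28) = 633. Under these assumptions, 80% power would need roughly 630 to 780 evaluable participants instead of 879.

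**7. The documents' own cut.** Using only below 1:10 versus 1:10 or above, R² for H3 is about 0.02 or less over the same correlations, so almost nothing is gained.

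**The case against.** The strongest reply is that nothing here is an error. Under randomisation the raw difference is unbiased, and its interval already includes chance imbalance: the 2.0 to 3.6 points lie inside the 7.0-point half-width and are not added to it. The trial meets its own 80% target. All of that stands. A reader might infer that the planned test is biased or has an inflated error rate, and the documents do not support that.

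A reader might also infer that the plan ignores Day 0 titre. It does not: the titre defines seroconversion, splits the secondary analyses, and is compared between arms, so an imbalance would be seen. What is missing is adjustment of the decisive comparison.

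The t-test sentence concerns GMTs and does not spell out how the ratio's interval is built. That the ratio is unadjusted is a reasonable inference from this sentence and the shells, and precision is not at stake there.

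Blood is drawn from everyone, but Protocol 4.1 requires HI testing only in a subset of at least 586 + 293 (the SAP synopsis says 630 + 315). This does not obstruct the remedy, because nobody can be classed for seroconversion without a Day 0 titre.

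Finally, the gain rests on an assumed correlation and an approximate model. That is a fair limit on the figures. The recalibration shows that the model's misfit to the H3 rate does not drive them.

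**Conclusion.** The point holds as a loss of efficiency and robustness in a valid analysis. It should be fixed, but the trial's conclusion does not depend on it. For H3 seroconversion, power at 586/293 would be about 84 to 91% instead of 80%, if the Day 0 to Day 21 correlation lies between 0.2 and 0.7, R² is similar in both arms, and the normal titre model is adequate.

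The larger seroconversion gains come at the lower correlations. The GMT variance reduction (about the squared correlation) grows with correlation, so the best cases for the two endpoints cannot occur together. For the GMT ratio, adjustment offers protection against chance baseline imbalance and no useful power.

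**What to change.** Prespecify the following in the SAP, before unblinding:

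- **Seroconversion (primary):** a baseline-standardised risk difference for each antigen, for example a logistic model on arm and ln Day 0 titre followed by g-computation, with the interval method named. If categories are preferred, use several titre levels, not only below 1:10 versus 1:10 or above.
- **GMT ratio (primary):** ANCOVA of ln Day 21 titre on arm and ln Day 0 titre, with the adjusted difference and its limits exponentiated.
- **Margins:** keep 10 percentage points and 1.5. Both adjusted estimates stay on the scales to which those margins apply.
- **Sensitivity:** report the unadjusted difference and ratio alongside.
- **Section 11.5:** replace the open-ended multivariate sentence with a reference to these models.

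The cost is SAP wording, a revision of TREF 02 to TREF 04 and a few lines of code. No new samples or data are needed, and the sample size can stay as planned.
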